1.1 Rap1 in the tumor microenvironment

Rap1, a small GTPase, suppresses metastasis by localizing at the plasma membrane of tumor cells through the process of prenylation, the post-translational attachment of a lipid tail. When Rap1 is localized at the plasma membrane of tumor cells, Rap1 promotes adhesion of the tumor cells and inhibits their metastatic spread. In contrast, when Rap1 prenylation is inhibited, Rap1 cannot anchor at tumor cell membranes, resulting in loss of cell-cell adhesion and increased metastasis of tumor cells.

Recently, it was discovered that prenylation of Rap1 is inhibited by activating adenosine receptors on tumor cells.^{1, 2} This was the first demonstration that Rap1 prenylation can be regulated by receptor activation.^{3, 4} Researchers subsequently discovered that prenylation of Rap1 is inhibited by activating ~~adrenergic~~ receptors (unpublished data). This discovery supports the novel model that beta-blockers will promote prenylation and membrane localization of Rap1, decreasing tumor aggressiveness. The demonstration that beta-blockers increase the prenylation of Rap1 will support future studies testing the effects of beta-blockers on the prenylation of Rap1 in patients' tumors. The aim of this study is to assess whether beta-blocker administration promotes Rap1 prenylation and membrane localization.

1.2 Beta-blockade and cancer

Retrospective epidemiologic studies have linked the use of beta-blockers to reduced rates of progression for several solid tumors.⁵⁻⁹ Recently, a retrospective case-control study of MM patients identified that concurrent use of any beta-blocker is associated with more favorable 5-year overall and disease-specific survival.¹⁰ Preclinical pharmacologic and biomarker studies in animals are now laying the groundwork for translation of beta-blockade as a novel adjuvant to existing therapeutic strategies in clinical oncology, linking the use of beta-adrenergic antagonists (beta-blockers) with reduced disease progression in humans.^{5-9, 11-18} Further, propranolol, a non-selective beta-adrenergic receptor blocker, has apoptotic and anti-proliferative effects on multiple myeloma (MM) cells.¹⁹ Propranolol is the most studied nonselective beta-blocker;²⁰ this, along with its safe side effect profile, cost-effectiveness, and efficacy *in vitro* in preventing tumor progression as compared to selective beta-antagonists^{16, 21, 22} make it our preferred beta-blocker for use in the current proposal. Propranolol does not have any significant drug interactions with the more common antineoplastic (melphalan) and infection-related drugs utilized to treat MM.

The first 30 days following autologous hematopoietic stem cell transplantation (HCT) generally constitute the time period around transplantation of greatest psychological and physiological stress and inflammatory processes.^{23, 24} Psychosocial stress gradually improves over time with a return to pre-transplant psychosocial functioning by about one year post-transplant.^{25, 26} Therefore, it follows that the first 30 days may also be the time

period of highest beta-adrenergic signaling due to increased stress response. Further, data from mouse models have demonstrated that beta-blockade with propranolol 8 days prior to exogenous stress exposure is effective in blocking beta-adrenergic signaling at the tumor level.¹⁷ Tumor metastasis in mouse models is increased 30-fold as compared to the control group after 20 days of exposure to chronic stress.²⁷

1.4 Rationale

This study will explore whether prenylation of Rap1 - recently identified as being under beta-adrenergic control - may be affected by beta-blocker use. Further, the proposed study addresses a major goal of the MCW Cancer Center; it promotes collaborative interactions between basic science researchers and clinicians at the Medical College. The proposed investigation of Rap1 prenylation will enhance the translational significance of [name] studies of Rap1 and may lead to future clinical trials of beta-blockers as novel therapeutic regulators of Rap1 in cancer.

2.0 STUDY DESIGN

This is a proof of concept randomized controlled pilot study assessing whether prenylation and membrane localization of Rap1 in PBMCs can be altered in individuals undergoing autologous HCT for MM by administering a daily beta-blocker (propranolol) to 20 participants. Outcomes of patients on this clinical trial will be compared to 20 participants in a control arm. Study assessment time points are detailed in Table 4.7a.

2.1 Primary Objective

The primary objective of this ancillary study is to explore whether beta-blocker administration will promote prenylation and membrane localization of Rap1 in peripheral blood mononuclear cells (PBMCs).

2.2 Patient Eligibility

Patients who are eligible for enrollment in the parent study.

2.3 Treatment Plan

Patients will be treated per the parent protocol.

3.0 STUDY ENDPOINTS

Western blotting on the cytosolic and membrane fractions of isolated PBMCs will determine the distribution of Rap1 in the different fractions as well as the status of Rap1 prenylation in the cells exposed vs. not exposed to beta-blocker therapy.

4.0 ENROLLMENT PROCEDURES

4.1 Patient Enrollment

Patients will be approached for this study during the pre-transplant evaluation phase. Transplant physicians will evaluate the patient eligibility onto the parent study and this ancillary study. Eligible patients willing to participate in the trial will sign an MCW IRB approved informed consent form. A Clinical Trials Office CRC will record the documentation of patient consent and proceed with registration procedures. All source documents that support eligibility including a signed informed consent/HIPAA and signed eligibility checklist, will be available, reviewed and eligibility verified. At the point of registration, a member of the study team will register the patient in the electronic database, including demographics, consent and on-study information. The patient will be assigned a unique sequence number for the study. The principal investigator (PI) of the study, [name], will be notified prior to enrollment. If at any point in time a patient wishes to withdraw from the study, they may notify [name] verbally or in writing. There will be no further data collection for participants who elect to withdraw from the study.

Target enrollment is 40 (20 per group) and includes patients undergoing autologous HCT for MM at MCW. Half of the participants in the parent study will be randomized via permuted block assignment with random block sizes to receive propranolol upon study entry. Informed consent will be obtained to access participants' full medical records to ascertain relevant demographic and medical data as outlined in Section 4.2. The patient must have signed informed consent prior to registration on both studies. Due to the pilot and feasibility nature of this study, the need to monitor response to prophylactic beta-

blocker usage in a medically ill population, as well as the objective nature of Western blot analysis, this pilot study will not be blinded. Patients will be enrolled by Day -7.. Total study duration will be up to 7 weeks for participants assigned to the intervention group (1 week pre-transplant through 6 weeks post-transplant) and 5 weeks for those in the control arm (1 week pre-transplant through 4 weeks post-transplant). Additional clinical information will be collected for 100 days post-transplant as identified in section 3.2.2.2.

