4.4 Specimen Collection

The Cancer Center Lab will draw one tube of blood to be stored in 8 mL BD Vacutainer CPT tubes at three study time points as described in Table 4.7b. These time points include baseline (Day -7), Day -2 (immediately prior to transplant, central line placement, or administration of any conditioning regimen), and Day +28. Blood will be drawn at one of two locations: in the hospital (if participants are immediately post-transplant and/or still or re-hospitalized) or in the transplant clinic during their regular visits. These 8 mL BD Vacutainer CPT tubes will be transferred to [name] lab at MCW for Western blot analysis. Before being transferred they will be assigned a dummy ID that will be the sole identifier of the samples. The linked identifiers will be stored on a secure computer network through the Clinical Trials Office under the PI's name.

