5.2 Sample Size and Power Calculation

We will enroll 40 participants undergoing autologous HCT for MM at MCW. Accounting for study attrition and beta-blocker intolerance, we aim to have 30 patients with a complete set of prenylation data. A targeted final sample of 15 participants in the intervention group will be sufficient for Western blot analysis. This sample size is established for the purpose of the parent study and should be sufficient to describe prenylation.

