5.3 Analysis of Primary Endpoints

5.3.1 Rap1 prenylation by beta-blocker exposure

Western blotting on the cytosolic and membrane fractions of isolated PBMCs will determine the distribution of Rap1 in the different fractions as well as the status of Rap1 prenylation in the cells exposed vs. not exposed to beta-blocker therapy. The statistical difference between cells from patients exposed to beta-blocker therapy (intervention arm) vs. those not exposed to beta-blocker therapy (control arm) will be determined by repeated-measures of analysis of variance (ANOVA) individually at the two blood assessment time points on beta-blocker therapy (Day -2, and Day +30). Baseline Rap1 prenylation will also be assessed by the first blood draw and may be compared to later time points. Patients will be included in final analyses if and only if they have been adherent to the study drug during the designated time period as described in the parent protocol.

References

2. Williams CL. A new signaling paradigm to control the prenylation and trafficking of small GTPases. *Cell Cycle*. 2013;12(18):2933-2934.
4. Linden J. Adenosine promotes tumor metastasis. *Sci Signal*. 2013;6(277):pe20.

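### Does the unblinded design leave the Western blot readings open to bias because laboratory masking is not spelled out?

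*Combined protocol and SAP*

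**What the plan says.** Section 4.1 (Patient Enrollment) describes randomisation to propranolol and then gives three reasons for not blinding. Two concern the type of study and the care of the patients: "Due to the pilot and feasibility nature of this study, the need to monitor response to prophylactic beta"-blocker use in people who are medically ill. The third concerns the assay: "as well as the objective nature of Western blot analysis, this pilot study will not be blinded". No exception is made for the laboratory.

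Section 4.4 (Specimen Collection) covers the tubes on their way to the laboratory: "Before being transferred they will be assigned a dummy ID that will be the sole identifier of the samples". It then places the key elsewhere: "The linked identifiers will be stored on a secure computer network through the Clinical Trials Office", under the principal investigator's name.

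Section 4.5 has laboratory members run the blots on the cytosolic and membrane fractions. Section 3.0 makes the blot the sole endpoint, including "the status of Rap1 prenylation in the cells exposed vs. not exposed to beta-blocker therapy". Section 5.3.1 tests it by arm: "The statistical difference between cells from patients exposed to beta-blocker therapy (intervention arm) vs. those not exposed".

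**The concern.** An open-label drug trial can still have a masked outcome reading, and the first two reasons in 4.1 bear only on the open-label part. The third is the only one that touches how the outcome is measured. A Western blot involves some handling choices, such as how bands are quantified, how they are normalised and when a blot is repeated, and the protocol sets no rule for any of these. On that view, calling the assay objective is an assertion.

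The hypothesis is also directional: section 1.1 expects beta-blockers to promote prenylation. If readers knew the arm, or if readings and repeats could still change after the link was opened, the one outcome of the study could drift towards the expected answer. A reader of the final report might be unable to tell whether that had been prevented.

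**Working it through.** The plan has no figure to reproduce here. Section 5.2 gives no alpha, power, effect size or SD. The check is therefore mainly a comparison of the sections, followed by a conditional calculation for scale.

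**Step 1: what the laboratory can see.**

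- Identity: under 4.4 the recoding happens before transfer and leaves one identifier on the tube. The name and the study sequence number assigned under 4.1 do not travel with it. A code that revealed the arm would not be a dummy code in any ordinary sense.
- Key: it is held through the Clinical Trials Office, not with the tubes.
- Draw schedule: 4.1 follows the intervention arm for up to 7 weeks and the control arm for 5 weeks, which could have given the arm away. It does not, because Table 4.7b schedules blood for blotting only at baseline, Day -2 and Day 28, with no split by arm. No tube is planned after Day 28 in either arm.

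Nothing the laboratory is planned to receive shows the arm.

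**Step 2: what the sentence in 4.1 covers.** It stands in the enrolment section, close to the randomisation text, and two of its three reasons concern treatment and care. It can be read as saying that patients and clinicians will know the arm, and that a laboratory measurement is less vulnerable to their knowing than a self-reported outcome would be. That reading fits 4.4. Reading it as a decision to unmask the laboratory would leave 4.1 at odds with the coding in 4.4.

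**Step 3: size if the readers did know the arm.** Inputs from the documents:

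- Section 5.2 aims for 30 complete sets, with 15 in the intervention group, so 30 − 15 = 15 controls.
- Section 4.1 enrols 20 per group.

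Assumptions not in the documents: no true drug effect, a constant reading shift of d SD in one arm, and a two-sided 5% two-sample t-test at one time point.

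The noncentrality is d × √(n/2), with 2n − 2 degrees of freedom. For n = 15, √7.5 = 2.739 with 28 df. For n = 20, √10 = 3.162 with 38 df.

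| Assumed shift d | Noncentrality, n = 15 | False positives, 15 per arm | In the expected direction only (nominal 2.5%) | False positives, 20 per arm |
|---|---|---|---|---|
| 0.1 | 0.27 | 5.8% | 4.5% | 6.1% |
| 0.2 | 0.55 | 8.3% | 7.6% | 9.5% |
| 0.3 | 0.82 | 12.5% | 12.2% | 15.2% |
| 0.5 | 1.37 | 26.2% | 26.2% | 33.8% |

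Simulation at 15 per arm gave 5.7%, 8.2%, 12.5% and 26.2%. The arithmetic is sound, but every row requires readers to know the arm, which Step 1 gives no reason to expect. With d = 0 the rate stays at 5%.

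**The case for a change.** The strongest case for a change is that the safeguard is implied and never stated. Section 4.4 does not describe the coding as masking, does not restrict who may see the link and sets no release time. Staff could open the link before repeat blots were finished without breaching any sentence of the protocol. The coding could equally have been meant only to protect privacy. Sections 2.3, 4.2 and 4.3 rely on the parent protocol, but 4.4 and 4.5 describe specimen handling and the assay without referring to it, so a rule there cannot be presumed. Masking also cannot be restored once it is lost.

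The textual part of this stands: no section states that the readers are masked or fixes when the link is opened. It does not show that readers will know the arm. Coding done for privacy still masks a reader who sees only the code. The lack of a quantification or repeat rule is a separate matter of assay detail and does not by itself make the readings arm-dependent. The aim also limits the stakes: sections 2.0 and 2.1 describe a proof-of-concept pilot meant to explore, and no error rate is claimed that could be breached.

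**Conclusion.** No change to the plan follows. The concern identifies missing detail, not a flaw in the design: the measure it asks for, coded samples with the key held outside the tube transfer, is already in section 4.4. Recording in the laboratory procedure or the final report that blots were read from codes, and when the link was opened, is ordinary good practice that does not depend on a protocol change.

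The false-positive rates should not be cited as a property of this trial. They rest wholly on assumed shifts. At 0.1 to 0.2 SD they stay between 5.8% and 8.3% with 15 per arm, and the larger values have no support in the documents.

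The conclusion assumes that 4.4 is carried out as written, that the codes carry no arm information, and that laboratory staff do not consult the link while readings can still change. Because names are removed, it cannot be confirmed from the documents that nobody in the laboratory has access to the link. The parent protocol was not available.

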4.2 Baseline Demographic-, Disease-, and Treatment-Related Variables

Same as the parent study

4.3 Data and Safety Monitoring Plan

Same as parent study.

4.4 Specimen Collection

The Cancer Center Lab will draw one tube of blood to be stored in 8 mL BD Vacutainer CPT tubes at three study time points as described in Table 4.7b. These time points include baseline (Day -7), Day -2 (immediately prior to transplant, central line placement, or administration of any conditioning regimen), and Day +28. Blood will be drawn at one of two locations: in the hospital (if participants are immediately post-transplant and/or still or re-hospitalized) or in the transplant clinic during their regular visits. These 8 mL BD Vacutainer CPT tubes will be transferred to [name] lab at MCW for Western blot analysis. Before being transferred they will be assigned a dummy ID that will be the sole identifier of the samples. The linked identifiers will be stored on a secure computer network through the Clinical Trials Office under the PI's name.

4.5 Rap1 prenylation

Peripheral blood mononuclear cells (PBMCs) will be isolated from the whole blood samples collected from patients at the three designated time points (Baseline, Day -2, and Day +28). Members of [name] laboratory (Professor, Pharmacology and Toxicology, MCW) will conduct western blotting on the cytosolic and membrane fractions of isolated PBMCs to determine the distribution of Rap1 in the different fractions, and the status of Rap1 prenylation in the cells.

4.6 Study Monitoring

The follow-up schedule for scheduled study visits is outlined in Table 4.7a with study assessment time points described in Table 4.7b.

TABLE 4.7a. FOLLOW-UP SCHEDULE

Study Assessment Time Point	Target Day
Baseline	Day -7 ± 2 days
Pre-Transplant	Day -2 ± 1 day ¹
4 weeks	28 ± 2 days

¹Assessment must occur prior to any conditioning regimen

TABLE 4.7b. PATIENT CLINICAL ASSESSMENTS

Study Assessments/ Testing	Baseline							
		-2	7	14	21	28	35	42
Blood draw for Western blot analysis	X	X				X		

5.0 STATISTICAL ANALYSIS

5.1 Study Design

5.1.1 Accrual

It is estimated that 9 months – 1 year will be necessary to enroll the targeted sample size.

5.1.2 Primary Endpoint

The primary endpoint is Day +28 (4 weeks) following HCT for MM, with intervention arm patients followed for an additional 1-2 weeks until they are weaned from beta-blocker therapy.

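### Section 5.1.2 makes Day +28 primary without attaching a Rap1 measure, and the ANOVA in 5.3.1, run separately at two visits, leaves Day -2 without a stated role and baseline optional

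*Combined protocol and SAP*

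**What the plan says.** **Section 5.1.2 (Primary Endpoint)** gives a time point and a follow-up arrangement: "The primary endpoint is Day +28 (4 weeks) following HCT for MM, with intervention arm patients followed for an additional 1-2 weeks". It names no Rap1 quantity.

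**Section 3.0 (Study Endpoints)** names the assay, Western blotting of PBMC fractions, and two readouts: "distribution of Rap1 in the different fractions as well as the status of Rap1 prenylation in the cells exposed vs. not exposed". It gives no formula, unit or visit. Both readouts match the primary objective in 2.1, which is to "explore whether beta-blocker administration will promote prenylation and membrane localization of Rap1".

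**Section 5.3.1**, under the heading Analysis of Primary Endpoints, compares the arms by repeated-measures ANOVA "individually at the two blood assessment time points on beta-blocker therapy (Day -2, and Day +30". On the baseline sample it says: "Baseline Rap1 prenylation will also be assessed by the first blood draw and may be compared to later time points".

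**Sections 4.4 and 4.5 and Table 4.7a** put the draws at baseline (Day -7 ± 2), Day -2 ± 1 and Day 28 ± 2. No draw is scheduled specifically for Day +30.

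**Section 5.2** enrols 40 and says "we aim to have 30 patients with a complete set of prenylation data", with 15 in the intervention group. It states no alpha, effect size or SD.

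**The concern.** Section 5.1.2 points to one day; the primary analysis section carries two, tested separately, and never says how the second relates to the first. An analyst following 5.3.1 literally would produce two arm comparisons and have to decide afterwards which one answers the objective.

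The two visits do not ask the same question. Section 1.2 says the first 30 days after transplant "generally constitute the time period around transplantation of greatest psychological and physiological stress and inflammatory processes", and reasons that they may also be the period of highest beta-adrenergic signaling. The Day -2 draw comes before any conditioning. Section 4.1 has the intervention arm randomized "to receive propranolol upon study entry". If dosing starts at the Day -7 draw (an assumption, because the start day is not given in this document), exposure is nominally -2 - (-7) = 5 days at the first on-treatment draw and 28 - (-7) = 35 days at the second. The results could reasonably differ.

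What is at stake is interpretation. Section 1.1 intends a positive result to support later Rap1 studies in patients' tumors. If the visits disagree in an unblinded pilot, a reader needs to know which comparison was planned as the main one. A second, smaller loss is that every patient gives a Day -7 sample that the planned comparison may not use.

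**Working it through.** The plan states no figure to reproduce for this point: no alpha, power, effect size or SD is given, and the sample size is taken from the parent study. The check is therefore a reading of the sections, followed by an illustration.

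**1. What the sections fix and leave open**

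| Element | 5.1.2 | 3.0 | 5.3.1 |
|---|---|---|---|
| Visit | Day +28 | none | Day -2 and Day +30 |
| Rap1 measure | none | two readouts, no formula | the same two readouts, no formula |
| Order of visits | Day +28 named primary | none | none |
| Baseline | not mentioned | not mentioned | optional |

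**2. Day +30.** The 4-week window is 28 - 2 = 26 to 28 + 2 = 30. Day 30 is the edge of the same visit, so this is a label slip and not another assessment.

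**3. Does the named method fit?** A repeated-measures ANOVA needs at least two values per patient. Taken at one visit there is one value per patient, and the two-arm ANOVA equals the two-sample t-test (F = t²; checked on generated data: 13.444 for both, p = 0.00102 for both). Repeated measures enter only if baseline or the other visit is in the model. The text makes baseline optional and separates the visits.

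**4. How often would the two comparisons disagree?** Illustration only.
- From the plan: 15 in the intervention group; 30 - 15 = 15 in the control group.
- Assumed: two-sided 5% per test, equal true effect of 0.8 SD at both visits, correlation r between visits of 0.3 to 0.8.
- Power of one test at 0.8 SD with 15 per arm: 0.562.
- P(exactly one significant) = 2 × [0.562 - P(both significant)].

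| r | Exactly one significant (simulated, 200,000 trials) | Implied P(both) = 0.562 - half of that |
|---|---|---|
| 0.3 | 0.403 | 0.36 |
| 0.5 | 0.338 | 0.39 |
| 0.8 | 0.208 | 0.46 |

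So even when the drug works equally well at both visits, the tests would split in about 21% to 40% of trials.

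**5. Cost of using baseline.** With 30 patients, a two-group comparison at one visit has 30 - 2 = 28 residual degrees of freedom; with baseline as a covariate, 27. The gain in precision depends on the correlation of baseline with Day +28, which the documents do not give.

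**The case against.** The strongest reply is that 5.1.2 already ranks the visits. It names one primary time in the singular, and 5.3.1 merely lists the analyses at both on-treatment draws; it never calls them co-primary. That stands. A reader might infer that 5.3.1 contradicts 5.1.2 and gives Day -2 equal primary standing, but this rests on a plural heading and the separate testing. What can be said is that the role of Day -2 is unstated where the primary analysis is described.

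Second, a reader might infer an inflated false-positive rate, or an estimate biased by reporting the larger of two differences. The documents support neither. The study is exploratory, states no alpha or success rule, and plans to analyze both visits.

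Third, the sentence on baseline allows workable readings, such as a baseline-to-visit ANOVA for each on-treatment draw. That is correct, and so the method is ill-specified rather than impossible. The t-test equivalence, and with it the illustration, holds only where baseline is left out.

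Fourth, the split results reflect low power at 15 per arm, and a better model would not abolish them. That also stands.

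Finally, one might want a single Rap1 readout made primary. Demoting membrane localization would rewrite the primary objective in the synopsis and 2.1. Section 1.1 describes membrane localization as occurring through prenylation, so the two are linked. Nothing in this point requires choosing between them.

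**Conclusion.** The point holds in a limited form. The primary endpoint is a day with no Rap1 measure tied to it, the primary analysis covers a second visit whose role is not stated, and the named ANOVA does not suit a single-visit comparison unless baseline is brought in, which the plan leaves optional. As written, 5.3.1 leads to two between-arm comparisons that it does not rank, and the Day -7 value may go unused.

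The size is illustrative: a split result in about 21% to 40% of trials, resting on 15 per arm, an assumed two-sided 5%, an equal 0.8 SD effect, visit correlation of 0.8 to 0.3, and no baseline adjustment. No stated figure in the plan is overturned. It should be corrected before any comparison by arm, because the repair is cheap and the day it makes primary is the protocol's own.

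**What to change.** **Section 5.3.1.** Replace the ANOVA sentence with:

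> One repeated-measures model will include arm, visit (Day -2, Day +28) and arm-by-visit, adjusted for the baseline (Day -7) value. The primary result is the arm difference at Day +28 (±2 days) with its 95% CI; the Day -2 difference is secondary and reported with its 95% CI.

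This also removes the Day +30 label and makes use of baseline definite.

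**Section 5.1.2.** Keep the existing sentence, including the intervention-arm follow-up, and add:

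> The Rap1 readouts of section 3.0 (prenylation status and membrane/cytosol distribution) are compared between arms at Day +28, with the quantification formula for each fixed before any comparison by arm.

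**Primary objective.** Leave prenylation and membrane localization both in place. Whether to rank one above the other is for the investigators.

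**Cost.** An amendment to the combined document, with no extra samples or visits. An effect seen only at Day -2 would count as secondary, though still reported. The adjusted model spends one degree of freedom on baseline. Split results between visits remain possible; the change settles in advance which one is primary.
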